## Study Summary

Title	A Real-world Study on the Efficacy and Safety of 9% Dexamethasone Insert in the Treatment of Postoperative Inflammation Following Cataract Surgery
Protocol Number	OT-502-002
Study Phase	Real-word Study
Study Duration	90 days
Study Center(s)	2 sites
Objectives	To evaluate the efficacy and safety of Dexamethasone Insert in the treatment of postoperative inflammation following cataract surgery in real-world clinical settings; and to evaluate the ease of use, time taken, and safety of the Dexamethasone Insert injector
Numbers of subjects	Plan: 263 subjects (113 subjects in the 9% Dexamethasone Insert group, 150 subjects in the external control group). Actual enrollment: 113 subjects in the 9% Dexamethasone Insert group, 150 subjects in the external control group; after propensity score (PS) 1:1 matching, 208 subjects (104 subjects in the 9% Dexamethasone Insert group, 104 subjects in the external control group) were included in the post-matching analysis.
Eligibility Criteria	
Inclusion Criteria:
 
 
1) Patients must be able to understand and sign the informed consent form (ICF), and be able to comply with all study procedures.
 
2) Male or female patients over 40 years old who planned to undergo phacoemulsification combined with intraocular lens implantation surgery.
 
 
Exclusion Criteria:
 
 
1) Known allergy to dexamethasone or any component of the Dexamethasone Insert.
 
2) History of endophthalmitis of any cause in either eye, presence of corneal abnormalities or malnutrition.
 
3) Patients with ocular hypertension, with an intraocular pressure (IOP) >21 mmHg in the study eye at screening, regardless of anti-glaucoma monotherapy.
 
4) Posterior capsule rupture or lens dislocation, anterior hyaloid membrane rupture, vitreous loss, and floppy iris syndrome during cataract surgery.
 
5) Other circumstances that, in the opinion of the investigator, the subject was not suitable for participation in the study
 

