The Ophthalmic Center of Boao Super Hospital relies on the advanced talents, technology, resources, and expert support of the Eye Hospital Affiliated to Wenzhou Medical University, covering all optometry disciplines, and shares resources with the Eye Hospital Affiliated to Wenzhou Medical University in clinical diagnosis, telemedicine, and joint discipline construction. Therefore, a real-world study on the efficacy and safety of the Dexamethasone Insert was conducted at the Ophthalmic Center of Boao Super Hospital, with research processes (including subject screening, Dexamethasone Insert operation, subject data generation, and postoperative follow-up) consistent with real-world clinical diagnosis and treatment standards, and the study results could be representative of real-world data.

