## 2. Overall Study Design and Plan

This was a prospective, real-world study. It was planned to prospectively collect the medical histories and follow-up data of 113 subjects who received Dexamethasone Insert in real-world settings in China, to evaluate the efficacy and safety of Dexamethasone Insert, and conduct a survey among 30 injector users on the ease of use, time taken, and safety of using the Dexamethasone Insert injector. Prospectively enrolled subjects returned to the study sites in Hainan for follow-up on Days 1, 8, 30, and 90 after Dexamethasone Insert injection. In addition to prospectively collecting data from subjects receiving Dexamethasone Insert as mentioned above, data from 150 cataract subjects previously treated using conventional clinical methods at selected medical institutions were also prospectively collected as an external control (conventional treatment) to further evaluate the efficacy and safety of the Dexamethasone Insert. Prospective collection of data of the external control subjects was conducted as consistently as possible with that of the Dexamethasone Insert group.

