### **4. Statistical Plan**

Descriptive statistics will be performed for de-identified demographic data, surgical details, clinical outcomes, and surgeon satisfaction.

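### Does reporting 104 matched pairs, when 113 were possible, point to a fault in the matched analysis?

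*Combined protocol and SAP*

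**What the plan says.** All the numbers are in the Study Summary, under the numbers of subjects. Enrolment is given as "Actual enrollment: 113 subjects in the 9% Dexamethasone Insert group, 150 subjects in the external control group". The next clause gives the matching as "after propensity score (PS) 1:1 matching", with the result that "208 subjects (104 subjects in the 9% Dexamethasone Insert group, 104 subjects in the external control group) were included in the post-matching analysis". The document contains nothing else about the matching: no covariates for the score, algorithm, caliper, common-support rule, replacement rule or handling of missing covariates.

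Section 2 (Overall Study Design and Plan) sets the aim in the full insert group, "113 subjects who received Dexamethasone Insert in real-world settings in China, to evaluate the efficacy and safety of Dexamethasone Insert", and describes the comparison group as "150 cataract subjects previously treated using conventional clinical methods at selected medical institutions". Section 4 (Statistical Plan) is a single sentence: "Descriptive statistics will be performed for de-identified demographic data, surgical details, clinical outcomes, and surgeon satisfaction". It does not mention matching and does not restrict reporting to matched subjects. In section 1 (Introduction), the remark that "the study results could be representative of real-world data" closes a sentence about study procedures following ordinary clinical practice.

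**The concern.** A reader who takes the ratio as the whole rule expects each of the 113 recipients to be paired with one of the 150 controls, leaving 37 controls over. The summary reports 104 pairs, so some further step removed 9 recipients, and the document does not name it.

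Who is matched settles whom an externally controlled comparison describes. If the 9 were removed because no control resembled them, the comparison covers a narrower group than the one in section 2. If they were removed for missing data, the question is completeness. If fewer controls were usable than were enrolled, the question is the quality of the control data. At stake is whether a result in 104 recipients can be read as a result for all 113.

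**Working it through.** **Inputs.** Insert recipients 113, controls 150, pairs 104 (all from the Study Summary). The document gives no endpoint, alpha, power, effect size or caliper, so anything below that needs one is an assumption.

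**1. The stated totals.** 113 + 150 = 263 and 104 + 104 = 208. Both agree with the summary.

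**2. The ceiling.** 1:1 matching without replacement and with no other restriction gives min(113, 150) = 113 pairs, leaving 150 − 113 = 37 controls. The reported 104 is below this:

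- recipients left out: 113 − 104 = 9, and 9/113 = 8.0%
- controls left out: 150 − 104 = 46, and 46/150 = 30.7%

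Some restriction was therefore applied. The figure 113 is the most that could be matched, not the number one should expect.

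**3. Is 104 an ordinary result?** Simulation with assumed normal scores on the logit scale, greedy nearest-neighbour matching and 300 runs per row. Without a caliper, every run gave 113 pairs. With an assumed caliper of 0.2 SD:

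| Assumed score difference between groups (SD) | Mean pairs | Central 95% of runs |
|---|---|---|
| 0 | 107 | 100 to 112 |
| 0.25 | 105 | 96 to 111 |
| 0.5 | 98 | 87 to 107 |
| 0.75 | 88 | 75 to 100 |
| 1.0 | 78 | 67 to 91 |

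The reported 104 lies inside the range for differences of 0 to 0.5 SD. Ordinary caliper matching of two modestly different groups would give about this number. This does not show that a caliper was used, only that 104 needs no unusual explanation.

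**4. How much the 9 can matter.** Let p be the response rate in the 104 matched recipients, for an assumed yes/no endpoint. The rate in all 113 lies between 104p/113 (none of the 9 respond) and (104p + 9)/113 (all respond):

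| Assumed p | Lower extreme | Upper extreme |
|---|---|---|
| 60% | 55.2% | 63.2% |
| 70% | 64.4% | 72.4% |
| 80% | 73.6% | 81.6% |
| 90% | 82.8% | 90.8% |

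These are limits that hold whatever the outcomes of the 9. If their rate differs from p by d points, the shift is d × 9/113:

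- d = 10: 0.8 points
- d = 20: 1.6 points
- d = 30: 2.4 points

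The same weight applies to a between-group difference. If the effect is D in the 104 and D + d in the 9, the average over 113 is (104D + 9(D + d))/113 = D + 9d/113.

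**The case for a change.** The strongest case for acting is that the reason for the loss is unknown, that the possible reasons mean different things, and that the matching is already done, so the sponsor must hold the answer. A flow line and a small table of the 9 beside the 104 would cost little. Nothing at this point is marked as redacted, so the silence is in the document itself.

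The facts in this stand: the counts are right and the restriction is not described. What does not follow is a defect in the plan. Naming the restriction would write down what was done; it would not alter the matched set or any estimate from it. It would not make the set reproducible either, because the score covariates, the algorithm and the handling of missing covariates are also unstated. A table of 9 subjects could show only gross differences.

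A second argument concerns safety. With no adverse event of a given kind, the one-sided 95% upper limit is 2.84% at 0/104 and 2.62% at 0/113, but a single case among the 9 would make it 4.13% at 1/113. This would matter if safety were confined to matched subjects. No text says so: section 2 sets the safety aim in all 113, and section 4 places no restriction on descriptive reporting.

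A third is that the document claims more reach than 104 recipients support. The Introduction's remark on representativeness rests on how the study was conducted, and the document states no comparative conclusion. It also does not call the matched set the main analysis. There is no overreaching statement to amend.

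**Conclusion.** The concern does not call for a change. The summary names a method and a ratio, 113 pairs is the maximum that ratio allows, and 104 is an unremarkable result once any usual restriction on match quality or data completeness applies. Leaving out recipients without an acceptable control is a normal trade-off: closer comparability in exchange for 8.0% of the treated group. No stated rule is contradicted, no better method is on offer, and the full insert group remains available for descriptive and safety reporting.

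The likely size is small: 0.8 to 2.4 points on a response rate if the 9 differ from the rest by 10 to 30 points. This rests on an assumed yes/no endpoint and assumed differences. The statement that 104 is ordinary rests on an assumed 0.2 SD caliper and normal score distributions; the document confirms neither. What remains is a missing detail of the kind the analyst supplies when reporting the matching.

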## 1. Introduction

Since the development of synthetic corticosteroids in the 1950s, corticosteroids have been used to treat eye disorders. They are important compounds for the treatment of inflammatory diseases. After entering cells, these compounds bind to glucocorticoid receptors, and are transported to the nucleus, activating the expression of anti-inflammatory genes, and inhibiting the expression of pro-inflammatory genes.

Dexamethasone was developed in the 1960s for the treatment of eye disorders and has since been used in ophthalmology. In current clinical practice, dexamethasone is used as a topical eye drop (in the form of a 1% ophthalmic suspension) to treat eye inflammation. Corticosteroid eye drops are commonly used to treat inflammation associated with cataract operations. Eye drops may need to be administered multiple times a day, presenting potential compliance issues; if compliance is poor, the expected therapeutic effect may not be achieved. As an alternative medication, dexamethasone delivered via short-term delivery systems can ensure subject compliance.

The Dexamethasone Insert, a new corticosteroid intraocular implant developed by EyePoint Pharmaceuticals in the United States (brand name DEXYCU®), was approved by the United States Food and Drug Administration (FDA) in February 2018 (approval number: NDA 208912) for the treatment of postoperative ocular inflammation. Under the support of the "National Nine Policies", drugs that have been approved for marketing in developed countries in Europe and America, not yet approved in China, and are urgently needed clinically, can be "piloted" in the Hainan Boao Lecheng International Medical Tourism Pilot Zone. In line with national spirit and the current urgent clinical needs domestically, the Hainan Provincial Health Commission and the Hainan Provincial Medical Products Administration have approved the use of the Dexamethasone Insert in the Hainan Boao Lecheng International Medical Tourism Pilot Zone.

The Ophthalmic Center of Boao Super Hospital relies on the advanced talents, technology, resources, and expert support of the Eye Hospital Affiliated to Wenzhou Medical University, covering all optometry disciplines, and shares resources with the Eye Hospital Affiliated to Wenzhou Medical University in clinical diagnosis, telemedicine, and joint discipline construction. Therefore, a real-world study on the efficacy and safety of the Dexamethasone Insert was conducted at the Ophthalmic Center of Boao Super Hospital, with research processes (including subject screening, Dexamethasone Insert operation, subject data generation, and postoperative follow-up) consistent with real-world clinical diagnosis and treatment standards, and the study results could be representative of real-world data.

## 2. Overall Study Design and Plan

This was a prospective, real-world study. It was planned to prospectively collect the medical histories and follow-up data of 113 subjects who received Dexamethasone Insert in real-world settings in China, to evaluate the efficacy and safety of Dexamethasone Insert, and conduct a survey among 30 injector users on the ease of use, time taken, and safety of using the Dexamethasone Insert injector. Prospectively enrolled subjects returned to the study sites in Hainan for follow-up on Days 1, 8, 30, and 90 after Dexamethasone Insert injection. In addition to prospectively collecting data from subjects receiving Dexamethasone Insert as mentioned above, data from 150 cataract subjects previously treated using conventional clinical methods at selected medical institutions were also prospectively collected as an external control (conventional treatment) to further evaluate the efficacy and safety of the Dexamethasone Insert. Prospective collection of data of the external control subjects was conducted as consistently as possible with that of the Dexamethasone Insert group.

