#### **3.2 Exclusion Criteria**

Subjects were not allowed to participate in this study if they met any of the following criteria:

- 1) Known allergy to dexamethasone or any component of the Dexamethasone Insert.
- 2) History of endophthalmitis of any cause in either eye, presence of corneal abnormalities or malnutrition.
- 3) Patients with ocular hypertension, with an IOP >21 mmHg in the study eye at screening, regardless of anti-glaucoma monotherapy.
- 4) Posterior capsule rupture or lens dislocation, anterior hyaloid membrane rupture, vitreous loss, and floppy iris syndrome during cataract surgery.
- 5) Other circumstances that, in the opinion of the investigator, the subject was not suitable for participation in the study.

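### Does Section 4 need an endpoint, unit and denominator for the injector objective, and a rule for operative events under exclusion criterion 4?

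*Combined protocol and SAP*

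**What the plan says.** The Study Summary joins a second aim to the main one on efficacy and safety: "to evaluate the ease of use, time taken, and safety of the Dexamethasone Insert injector".

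Section 2 (Overall Study Design and Plan) splits the work in one sentence. To assess the Insert itself, the study will "prospectively collect the medical histories and follow-up data of 113 subjects who received Dexamethasone Insert in real-world settings in China". For the injector it will "conduct a survey among 30 injector users on the ease of use, time taken, and safety of using the Dexamethasone Insert injector".

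The Study Summary also reports the propensity-score result: "208 subjects (104 subjects in the 9% Dexamethasone Insert group, 104 subjects in the external control group) were included in the post-matching analysis".

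Section 4 (Statistical Plan) reads in full: "Descriptive statistics will be performed for de-identified demographic data, surgical details, clinical outcomes, and surgeon satisfaction". It does not mention the survey.

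Section 3.2, criterion 4, excludes subjects with "Posterior capsule rupture or lens dislocation, anterior hyaloid membrane rupture, vitreous loss, and floppy iris syndrome during cataract surgery". It does not say how such an event relates in time to the use of the injector.

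**The concern.** A stated objective with no line of its own in the analysis section is a fair thing to query. Section 4 gives no scale, no start and stop for timing, no definition of an injector problem, and neither unit nor denominator. The nearest item, surgeon satisfaction, is not tied to the survey, and satisfaction is a different thing from time taken or safety. Three counts appear in the documents (30 users, 113 Insert subjects, 104 matched Insert subjects). A share of users reporting a problem is not a rate per injection, and a reader could take one for the other.

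Criterion 4 adds a second worry. If the injector is used within the operation, a capsule rupture or vitreous loss at injection would meet the exclusion as worded. Removing that subject would take the event out of both numerator and denominator, and injector safety could then look clean for the wrong reason. The documents report no number excluded under this criterion.

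**Working it through.** **1. Which set serves which purpose.** The documents give no derivation for 30, 113 or 150, so there is no sample-size figure to reproduce. The totals agree: 113 + 150 = 263 and 104 + 104 = 208.

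| Set | Where | Purpose stated |
|---|---|---|
| 30 injector users | Section 2 | all three injector items |
| 113 Insert subjects | Section 2 | efficacy and safety of the Insert |
| 104 matched Insert subjects | Study Summary | post-matching analysis against external controls |

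The three survey topics in Section 2 are the three parts of the injector objective in the Study Summary. Nothing links the 104 to the injector, and nothing says that the 113 are a second source for injector safety. The documents therefore point to one set, the users.

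**2. What would be at stake if the set were open.** With zero events in n independent units, the exact two-sided 95% upper limit is 1 − 0.025^(1/n):

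- n = 30: 1 − 0.025^(1/30) = 11.6%
- n = 104: 1 − 0.025^(1/104) = 3.5%
- n = 113: 1 − 0.025^(1/113) = 3.2%

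One event would read as 1/30 = 3.3% or 1/113 = 0.9%. The gap is real arithmetic, but the first line concerns users and the other two concern patients. They are not rival estimates of one quantity.

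**3. Clustering.** Injections by the same user may be correlated. If 113 injections were spread evenly over 30 users (an assumption), each user made 113/30 = 3.77. The design effect is 1 + (3.77 − 1) × ICC, so a design effect of 3 would need ICC = 2/2.77 = 0.72, which is extreme. In any case this bears on a per-injection rate, which the plan does not propose.

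**4. Criterion 4.** For it to distort the injector result, three things must all be true:

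- the injector is used within what the criterion calls cataract surgery (the documents do not say when it is used);
- an entry exclusion was applied to subjects who had already been injected (not stated);
- injector safety is a count over subjects (Section 2 makes it a survey of users).

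The third fails on the text. Excluding a patient does not, by its terms, remove a surgeon's survey answer. If all three are nevertheless assumed, and k subjects were removed in addition to the 113, a reported 0% would really be 1/114 = 0.9% for k = 1 or 3/116 = 2.6% for k = 3. The documents give no k, and k = 0 changes nothing.

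**5. What an analyst would do with Section 4 as written.** The plan is descriptive throughout. Given completed questionnaires from injector users, the analyst tabulates each of the three items over the users who answered, and reports the number answering. No other reading of the survey produces a different headline result.

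**The case for a change.** The best argument for a change is that a descriptive rate still needs a unit and a denominator, and Section 4 states neither for an objective that the Study Summary sets beside efficacy and safety. Surgical details might hold injection times or operative problems, but the text does not say so. Section 2 describes the 113 as subjects who received the Insert, which leaves failed attempts unaddressed. With planned and actual Insert enrolment both given as 113 and no count of exclusions, a reader cannot check whether any subject left under criterion 4.

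Part of this stands. The survey has no stated scale, timing definition or definition of a problem, and Section 4 does not connect surgeon satisfaction to it. The documents also do not say how failed attempts are treated.

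The rest does not carry a change. The silence of Section 4 is not particular to the injector: one sentence covers every objective, efficacy included. Timing per attempt, a count of failed attempts and a before-and-after split of exclusions would be new endpoints for a descriptive user survey. They would depend on records that the documents do not show to exist. The Introduction lists "research processes (including subject screening, Dexamethasone Insert operation, subject data generation, and postoperative follow-up" among the research processes, but that does not show that times, failed attempts or reasons for removal were written down. The Study Summary already reports actual enrolment, so what was not recorded cannot now be obtained.

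**Conclusion.** No change to the plan is needed. Section 2 settles the source and the respondent for the injector objective, and the missing detail is of a kind that an analyst fills in the obvious way: three items, summarised over responding users, with the results read as user-reported. The difference between 11.6% and 3.2% shows that unit matters in general. It does not measure an error here, because the plan does not put the 113 or the 104 forward for this purpose.

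The criterion 4 concern is an ambiguity of wording with no demonstrated effect. It depends on three conditions that the documents do not state, one of which runs against Section 2.

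This conclusion rests on taking Section 2 at its word that the injector items come from the survey. If injector safety were instead reported as a rate per subject or per injection, the questions about denominator and exclusions would become live. The comparison with the external control group is untouched either way.

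### Does the unstated place of treatment of the 150 external controls mean that the plan needs a within-site comparison?

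*Combined protocol and SAP*

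**What the plan says.** The Introduction ties permission to use the product to one area: the provincial authorities "have approved the use of the Dexamethasone Insert in the Hainan Boao Lecheng International Medical Tourism Pilot Zone". It then places the study at a single centre: "a real-world study on the efficacy and safety of the Dexamethasone Insert was conducted at the Ophthalmic Center of Boao Super Hospital". Section 2 uses the plural, saying that Insert subjects "returned to the study sites in Hainan for follow-up on Days 1, 8, 30, and 90 after Dexamethasone Insert injection".

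For the comparison arm, Section 2 says that "data from 150 cataract subjects previously treated using conventional clinical methods at selected medical institutions were also prospectively collected as an external control", and adds: "Prospective collection of data of the external control subjects was conducted as consistently as possible with that of the Dexamethasone Insert group".

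The Study Summary counts two sites without splitting them by arm. It reports that "after propensity score (PS) 1:1 matching, 208 subjects" ("104 subjects in the 9% Dexamethasone Insert group, 104 subjects in the external control group") entered the matched analysis, and lists no propensity score covariates. Section 4, the whole statistical plan, is a single sentence that limits the analysis to descriptive statistics. It does not mention site.

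**The concern.** An external control treated at other hospitals can differ from the treated arm in surgeon, technique, perioperative care and grading of inflammation. Propensity score matching on patient characteristics would neither remove nor reveal such differences. In the extreme case, with all Insert subjects at one site and all controls at another, the matched difference estimates the Insert effect plus the site effect and cannot separate them. Because the controls were added to support further judgement of efficacy and safety, a reader wants to know how close the study is to that case.

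The site statements permit at least three readings:

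- Both sites supplied both arms.
- One site supplied each arm.
- The count of two covers only the Insert sites and leaves out the institutions that supplied 150/263 = 57.0% of subjects.

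With no planned analysis by site, it is natural to ask for one.

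**Working it through.** **Inputs.** Study Summary: 113 Insert subjects, 150 controls, 104 matched in each arm. Section 2: 150 controls. The number of controls treated at Insert sites, m, is not given and is varied below as an assumption.

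**Stated totals.** 113 + 150 = 263 and 104 + 104 = 208; both agree with the document. The matched set holds 104 distinct controls, so 150 − 104 = 46 controls are unused.

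**Bound on within-site pairs.** With 150 − m controls from elsewhere, of whom at most 46 can be left out, the fewest possible cross-site pairs is max(0, 150 − m − 46) = max(0, 104 − m). It reaches zero only if m is at least 104, and 104/150 = 69.3%. If matching ignores site and all Insert subjects are at one site, the expected number is 104(150 − m)/150.

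**Precision of a within-site estimate.** Assume that all 104 matched Insert subjects are at one site, that all m controls there are used, and that outcome variance is equal in both arms. Relative to 104 against 104, the SE ratio is √[(1/104 + 1/m)/(2/104)] = √[(1 + 104/m)/2].

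| m (assumed) | Fewest cross-site pairs | Expected if matching ignores site (one Insert site) | SE ratio |
|---|---|---|---|
| 104 | 0 (0%) | 31.9 (30.7%) | 1.00 |
| 75 | 29 (27.9%) | 52.0 (50%) | 1.09 |
| 50 | 54 (51.9%) | 69.3 (66.7%) | 1.24 |
| 10 | 94 (90.4%) | 97.1 (93.3%) | 2.39 |
| 5 | 99 (95.2%) | 100.5 (96.7%) | 3.30 |
| 0 | 104 (100%) | 104 (100%) | no estimate |

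**What drives the bias.** A 1:1 matched mean difference is the Insert mean minus the control mean, so who is paired with whom drops out. For two sites that differ additively by d, the bias is d(p_I − p_C), where p_I and p_C are the proportions of each matched arm at the first site.

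- *One Insert site.* p_I = 1, and p_C is the share of matched controls treated there. The gap 1 − p_C equals the cross-site share, so the table can be read as bias.
- *Two Insert sites, both arms split 52/52.* The gap is 0.5 − 0.5 = 0, so there is no bias. Pairing that ignores site still gives about 104 × 0.5 = 52 cross-site pairs, in opposite directions that cancel. Here m = 150, and the formula 104(150 − m)/150 would return 0 cross-site pairs. It neither counts the pairs correctly nor explains why the bias is nil.

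The plural sites in Section 2 make the second case a live possibility. In that case 69.3% is necessary but not sufficient for all pairs to be within-site, because controls must also be available and matchable at each site separately.

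**The three readings.** If both sites supplied both arms, the gap may be small or nil, and a stratified estimate may add little. If each site supplied one arm, the gap is 1 and no within-site estimate exists, so planning one achieves nothing. If the control institutions lie outside the count of two, the gap is unknown.

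**The case for a change.** The best argument for a change is that the remedy needs no new subjects while the risk is total confounding. The matched set is the only comparative dataset described. The promise of consistency in Section 2 concerns data collection, and if the controls had already been operated on, consistent collection cannot align their surgery. The Introduction's list of aligned research processes concerns the Insert study at Boao. On this argument, a site count by arm, a covariate list and a site-stratified result are little to ask.

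Much of this is right as description. The documents do not say where controls were treated or whether site was in the propensity score, and a reader cannot judge confounding with site without that. The step to a change in the plan is weaker, for three reasons.

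- The text is mixed on whether control surgery was in the past. Section 2 calls the controls previously treated but also says their data were gathered prospectively, and Section 3.1 requires consent and a planned operation.
- Silence about site in the propensity score does not show that site was left out. The covariates are not listed at all, so site is one unstated element among several.
- A rule that distrusts the overall result whenever a stratified result differs has no threshold. At m = 10 the stratified SE is 2.4 times as large, so the two would often differ by chance.

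**Conclusion.** No change to the plan follows. This is missing detail that analysts ordinarily supply when they report: subjects by arm and site before and after matching, and the variables in the propensity score. Nothing in the documents shows that overlap was low, that site was ignored in matching, or that the analysis gives a wrong answer. Depending on an assumed m, the unavoidable cross-site share is anything from 0% (m of 104 or more) to 100% (m = 0). It equals the share of a site difference entering the result only if all Insert subjects were at one site and the site difference is additive.

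A mandatory within-site estimate is not a clear gain. It may add little where site mix is already balanced and is impossible where no site treated both arms. In between, its SE is 1.09 to 3.3 times as large for m from 75 down to 5, under equal variances and one Insert site. Section 4 promises only descriptive statistics, and the Study Summary already reports enrolment and matching as done, so what remains is presentation and interpretation. If the arm-by-site counts turn out to show no site with both arms, the comparative conclusion has to be read with that limit. That is a matter for the report and does not show a fault in the plan.
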